2.3.1.1 Individual benefits

Expected patient benefits are:

- A significant decrease in the occurrence of postoperative infection.
- A significant decrease in hospital length of stay.
- A significant decrease in both postoperative mortality and morbidity.
- A significant decrease in exposure to antibacterial agent which could be harmful (as clostridium difficile colitis).

2.3.1.2 Collective benefits

Since the menace of complete absence of effective antibiotics to treat problematic hospital acquired infections exists, our study will participate to the development of innovative treatment and prophylactic approaches. Thus, expected public health benefits (or collective benefits) are:

- Clear benefits for public health since healthcare associated infections in hospitals impose significant economic consequences on the nation's healthcare system.

- A decrease in the emergence of resistant strains in surgery, hospital and general population since postoperative infections are responsible for antimicrobials prescription which is the single most important cause of the emergence of drug resistance, both in the community and hospital settings.

2.3.2Risks

No specific risks (individual or collective) are likely to occur:

- Maintaining MV during CPB did not hamper surgical procedure ;

- Several studies have found benefits to maintain MV, mainly in biological parameters; however no study has demonstrated its impact on postoperative infections.

2.3.2.1 Individual risks

Physical risks and constraints

Main constraints are blood withdrawn from patients. However, volume withdrawn will not induce any physical side effect.

Psychological risks and constraints

The patients will not present any specific psychological risks or constraints associated with this study. The psychological risks to the patients included in this trial are the same as for any patient requiring cardiac surgery.

Socio-economic risks and constraints

The patients will not present any specific socio-economic risks or constraints associated with this study. The psychological risks to the patients included in this trial are the same as for any patient requiring cardiac surgery.

2.3.2.2 Collective risks

None.

2.3.3Benefit / risk ratio

Given the expected benefits and low specific risks, the benefit/risk ratio is highly favourable.

2.4 Statement indicating that the study will be conducted in compliance with the protocol as well as with good clinical practices and legislative and regulatory conditions in force

The sponsor and the investigator also agree that this study will be conducted:

- in compliance with the protocol,
- in compliance with local and international good clinical practice currently in force,
- in compliance with legislative and regulatory conditions currently in force in participating countries.

2.5 References to the scientific literature and to relevant data used as a reference for the study See appendix 2

3 STUDY OBJECTIVES

3.1 Primary objective

To measure the incidence of postoperative infections in 2 groups of patients: one group of patients ventilated and one group of patients without mechanical ventilation during cardiopulmonary bypass for cardiac surgery, and demonstrate that the incidence of postoperative infections is significantly lower in patients ventilated during CPB.

3.2 Secondary objectives

To demonstrate that, compared to patients without MV during CPB, maintaining MV will:

- Decrease postoperative immunodepression (human leukocyte antigen-DR antigen (HLA-DR) expression on monocytes, Indoleamine 2,3-Dioxygenase (IDO) activity, plasmatic levels of IL-10 and proportion of myeloid-derived suppressor cells (MDSCs));
- Decrease postoperative inflammation (plasmatic levels of IL-6 and quantity of extracellular vesicles (EV);
- Decrease the occurrence of lymphopenia after surgery (defined as an absolute lymphocyte count less than 1.2 cells/ μ L × 10.3);
- Decrease postoperative exposure to antimicrobials treatment;
- Decrease postoperative mortality;
- Decrease postoperative length of stay;
- Increase the PaO2/FiO2 ratio after surgery;
- Decrease postoperative duration of MV.

4 STUDY DESIGN

4.1 Study evaluation criteria

4.1.1Primary evaluation criteria

Primary end point will be the incidence of postoperative infections (ie nosocomial infections) within 28 days following cardiac surgery. The diagnosis of a postoperative infection will be based on clinical, biochemical, or morphological features and confirmed (if possible) by bacteriological data according to CDC definitions for nosocomial infections (appendix 7).

4.1.2Secondary evaluation criteria

Immunomonitoring:

- Postoperative expression of HLA-DR on peripheral monocytes at day 0, day 1 and day 7, Postoperative levels of IL-10 at day 0, day 1 and day 7, Postoperative indoleamine 2,3-Dioxygenase (IDO) activity at day 0, 1 and 7 Postoperative proportion of MDSCs at day 0, day 1 and day 7;
- Postoperative levels of IL-6 at day 0, day 1 and day 7, Postoperative quantity of EV at day 0 and day 1;
 - Postoperative lymphocytes count at day 0, 1 and 7;
- Number of days of exposure to each antibiotic per 1000 inpatient days, defined as the number of days (>24 h) of continuous antibiotic treatment (from days 1 to 28); duration of antibiotic treatment;
- Mortality within 28 days following surgery ;
- Hospital length of stay (max 28 days) defined as the number of days before first hospital discharge;
- PaO2/FiO2 ratio at day 0 and day 1;
- Duration of MV (max 28 days).

4.2Description of study methodology

4.2.1Experimental design

A prospective, multicenter, single-blind, randomized, parallel-group trial.

4.2.2Conduct of study

4.2.2.1. Screening phase

During the day of the consultation with a cardiac surgeon, the patients fulfilling the inclusion criteria and after verification of the exclusion criteria, will be proposed to participate to the study. Informed consent will be obtained during the consultation. If necessary, after this information session the patient can reconsider his/her decision within a period of time.

4.2.2.2. Inclusion phase

The patients will be randomized the day of surgery before induction of anesthesia.

Data collected at inclusion: The following data were collected: age, sex male, body mass index (BMI), EuroScore, type of surgery (isolated coronary artery bypass graft (CABG), single valve, surgery on multiple valve, CABG plus valve), coexisting medical conditions (Hypertension, diabetes mellitus, previous cerebrovascular event (stroke/transient ischemic attack), peripheral vascular disease, preoperative creatinine, chronic renal dysfunction), antibiotic prophylaxis.

Description of surgery:

- General anesthesia will be induced with propofol and sufentanil (or remifentanil) and will be followed by cisatracurium for muscular relaxation. Anesthesia, muscle relaxation, and analgesia will be respectively maintained with inhaled sevoflurane during off-pump surgery or propofol infusion during CPB and boluses of atracurium and sufentanil (or remifentanil).
- For baseline ventilation, the patients will receive volume-controlled ventilation with a tidal volume of 6-8 mL/kg of predicted body weight and a ventilatory frequency of 10 to 15 per minute (end-tidal carbon dioxide between 34 and 38 mmHg). Inspired oxygen fraction (FIO2) will be adjusted to ensure a peripheral oxygen saturation of > 92%, inhalation-to-exhalation ratio will be 1:2, and the level of PEEP will be 5-7 cmH2O.
- During CPB, two settings will be used depending on the study arm:
 - In the control group (MV- group): absence of MV (and no PEEP) by disconnecting the tracheal tube from the ventilator;
 - In the MV + group: dead space ventilation using tidal volume of 2.5 mL/kg/pbw (predicted body weight) with 5-7 cmH2O PEEP.
- After CPB, a recruitment maneuver will be performed. Recruitment maneuver consisted of applying a continuous positive airway pressure of 30 cm of water for 30 seconds, and then ventilatory parameters will be turned back to

baseline settings. All postoperative patients will be admitted to the intensive care unit (ICU) and will be ventilated with volume-controlled ventilation, VT=6-8 ml/Kg/pbw, FiO2 of 60% and PEEP of 5cmH2O.

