1.10 Independent validation committee

The validation committee will include 3 members, an infectiologist, a bacteriologist, and an intensivist. They will be in charge to validate the occurrence of nosocomial infections and the date of occurrence and will be blinded to the study arm (blinded evaluation of the primary endpoint). They will be provided with a standardized patient record containing all required document necessary harmonize patients' evaluations.

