4.2.2.3. Follow-up

Data collected after surgery: duration of procedure, duration of CPB, duration of aortic cross-clamping, antibiotics treatments, duration of MV, length of stay in ICU, hospital length of stay, mortality.

Immunomonitoring parameters (HLA-DR expression, IL-10 and IL-6, lymphocytes count, Indoleamine 2,3-Dioxygenase activity, MDSCs and EV) will be obtained after general anesthesia and before surgery (D0, at 24 hours (D1) and 7 days (D7) (except EV) after surgery.

HLA-DR expression, IL-10, IL-6 and IDO activity will be measured in Rennes.

Ratio of arterial oxygen tension (PaO2) to FIO2 will be obtained before surgery (D0) after induction of anesthesia and 3 h after the end of CPB in the surgical intensive care unit (ICU; under baseline MV settings), and the day after surgery (D1).

Occurrence of postoperative infections within 28 days following cardiac surgery will be monitored. An independent committee blinded to treatment group will ensure the classification of hospital-acquired infections. Antibiotics treatment, length of stay, duration of MV, mortality will be recorded within the first 28 days following surgery.

	Screening Phase	Inclusion Phase (D0) Surgery	D1	D7	D28
Information document	Х				
Clinical Examination (check the selection criteria)	X				
Written informed consent	Х	Or X (later)			
Randomization		Х			
Patient characteristics and clinical data		Х			
Data surgery		Х			
HLA-DR* and MDSCs*		Х	Х	Х	
IL-10*		Х	Х	Х	
IL-6*		Х	Х	Х	
IDO activity*		Х	X	X	

EV*	Х	X		
Lymphocytes count	Х	X	X	
Pa02/Fi02	X After induction of anesthesia and 3 h after the surgery	Х		
Nosocomial infections recording		Х		
Antibiotics treatment	Х			
Lenght of stay X				
Duration of MV		X		
Mortality	Х			
Adverse events recording	X			

* HLA-DR expression, MDSCs, EV, IL-10, IL-6 and IDO activity will be measured in Rennes.

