4.3 Description of the measures taken to reduce and prevent bias

4.3.1 Randomization

Randomization will be stratified per centre.

Randomization will be performed in the centres via a webinterface (Ennov Clinical, Ennov Group, Paris, France). A document to help use this tool will be provided to the investigators.

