4.3.2 Methods of blinding

This project is a randomized single-blinded (patient) trial.

4.4 Expected duration of participation of persons and description of chronology and of duration of all study periods including monitoring, if applicable

Recruitment period: 24 months

Duration of patient monitoring: 28 days

Duration of analysis of data: 6 months

Estimated total duration of study: 31 months

Starting with inclusion of the first patient, the sponsor has to inform without delay the local health agency and the ethics committee of the actual date of start-up of the study. The actual date of start-up = date of signature of consent form by the first person who is a Patient in the study.

The date of end of the study will be transmitted by the sponsor to the ethics committee and to the local health agency within 90 days or earlier according to local regulations. The date of end of the study corresponds to the last visit of the last person who is a Patient in the study.

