Our hypothesis is that 15% of the patients without MV during CPB (MV- group) will have post-operative infection at day 28. A total sample size of 1392 patients (696 per group) is required to achieve 80% power to detect a decrease in the rate of postoperative infection in patients with MV during CPB (MV+ group) to 10%, using a two-sided test with a type I error of 5% (nTerim, V4.0, Statistical solutions Ltd, Cork, Ireland), **1400 will be included to take into account potential non evaluable patients (death during surgery, lost to follow-up...).**

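### Randomisation precedes induction although the arms differ only during CPB, and nothing says the arm is withheld from the operating team until then: a cheap change of timing would protect the baselines and keep out most patients who never reach CPB.

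*Combined protocol and SAP*

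**What the plan says.** **Time of randomisation.** Section 4.2.2.2 reads "The patients will be randomized the day of surgery before induction of anesthesia". Section 4.3.1 adds "Randomization will be performed in the centres via a webinterface", stratified by centre. It does not say who logs in, who sees the result, or when.

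**Where the arms part.** Section 4.2.2.2 gives one anaesthetic regimen and one set of baseline ventilation ranges for everyone. Only for the CPB period does it say that "two settings will be used depending on the study arm". The recruitment manoeuvre afterwards is again common to both arms.

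**Baselines.** In section 4.2.2.3 the immunomonitoring samples "will be obtained after general anesthesia and before surgery (D0", and for oxygenation: "Ratio of arterial oxygen tension (PaO2) to FIO2 will be obtained before surgery (D0) after induction of anesthesia". A further PaO2/FiO2 follows 3 h after the end of CPB and another on D1.

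**Blinding.** Section 4.3.2: "This project is a randomized single-blinded (patient) trial". Section 1.10 adds that the members of the validation committee "will be blinded to the study arm (blinded evaluation of the primary endpoint".

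**Who is randomised and analysed.** Under section 5.1, eligibility rests on surgery being scheduled with CPB, aortic clamp and cardioplegia. Sections 8 and 8.5 analyse patients who are both randomised and evaluated. Section 8.2 requires 1392 and says "1400 will be included to take into account potential non evaluable patients (death during surgery, lost to follow-up". No section says how a patient who is randomised but not put on CPB is handled.

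**The concern.** Between randomisation and the start of CPB there is an interval in which the arms should not differ at all. The plan takes its baselines in that interval and specifies nothing to keep the arm from the people working in it. Two consequences follow.

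First, the D0 values are measured after allocation. They enter the time-by-group repeated-measures analysis of section 8.1.4, which also allows adjustment for heterogeneity at inclusion. A baseline is best fixed before anyone measuring it can know the arm. PaO2/FiO2 is the most exposed because the team sets its denominator, titrating FiO2 to a saturation target, and PEEP may vary within 5-7 cmH2O.

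Second, allocating this early admits patients whose operation changes before CPB. They cannot receive the contrast under test. If analysed they dilute it; if treated as not evaluated they draw on a small reserve.

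No section gives a reason for allocating before induction.

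**Working it through.** **Step 1. Order of events on D0**, from sections 4.2.2.2 and 4.2.2.3:

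| Order | Event | Do the arms differ? |
|---|---|---|
| 1 | Web randomisation | – |
| 2 | Induction and baseline ventilation | No |
| 3 | First D0 PaO2/FiO2; D0 immune samples | No |
| 4 | Surgery up to CPB | No |
| 5 | CPB | Yes, first difference |
| 6 | Recruitment manoeuvre, ICU; PaO2/FiO2 at 3 h | Same rules, arm already delivered |

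Steps 2 to 4 come after allocation and before any difference in treatment. The D0 column of the schedule table marks randomisation and sampling together without an order, so the order comes from the text.

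**Step 2. Which baselines are exposed.** HLA-DR, IL-10, IL-6, IDO activity, MDSCs and EV are laboratory values measured in Rennes, on samples drawn before the arms differ. The first PaO2/FiO2 depends on bedside settings. The primary test (section 8.1.3) is a Chi² test on infection and uses no D0 value.

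**Step 3. The plan's own sample size.** Inputs from section 8.2: 15% versus 10%, two-sided 5%, 80% power, 696 per group.

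With mean rate 0.125, pooled variance and no continuity correction,

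n per arm = [1.960 × √(2 × 0.125 × 0.875) + 0.8416 × √(0.15 × 0.85 + 0.10 × 0.90)]² / 0.05² = 685.6, so 686 per arm and 1372 in total.

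The stated 1392 is 1.4% higher. Simulating the three looks at the significance levels of section 8.1.3 gives 80.1% power at 696 per arm, so 1392 is consistent with the fixed design plus an allowance for the interim analyses. The figure reproduces.

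**Step 4. The reserve.** 1400 − 1392 = 8 patients; 8/1400 = 0.57%.

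**Step 5. Dilution by patients who never reach CPB.** Let f be the share randomised but not put on CPB. The documents give no value, so f is an assumption. Assume also that such patients have the 15% rate in both arms. Then:

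- MV+ rate: p₂ = 0.10(1 − f) + 0.15f
- Difference: d = 0.05(1 − f)
- Power: Φ[(d − 1.960·s₀)/s₁], with p̄ = (0.15 + p₂)/2, s₀ = √[2p̄(1 − p̄)/696] and s₁ = √[(0.15 × 0.85 + p₂(1 − p₂))/696]

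For f = 0: s₀ = 0.017728 and s₁ = 0.017678, giving Φ(0.863) = 80.6%.

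| Assumed f | Patients of 1400 | Difference (points) | Fixed-design power, 696 per arm | Three-look power at 1400, kept | Three-look power at 1400, dropped |
|---|---|---|---|---|---|
| 0 | 0 | 5.00 | 80.6% | 80.4% | 80.4% |
| 1% | 14 | 4.95 | 79.7% | 79.5% | 80.0% |
| 2% | 28 | 4.90 | 78.9% | 78.6% | 79.6% |
| 3% | 42 | 4.85 | 78.0% | 77.7% | 79.2% |

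The size of any bias from knowing the arm before CPB cannot be derived from the documents.

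**The case against.** **Disclosure is inferred.** A reader might conclude that the allocation is revealed before induction and that the team knows it. The documents do not say so. They fix the time of randomisation and are silent on who receives the result. This stands: the defect is that no concealment until CPB is specified. With randomisation done in the centres and only the patient blinded among those in the operating room, early knowledge is likely but not stated.

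**The interval is largely protocolised.** Section 4.2.2.2 sets the anaesthetic agents, tidal volume, frequency, end-tidal CO2, inspiratory ratio and PEEP range. Sections 6.1 and 6.3 are general permissions, not specific to this interval. It would be too much to say that all care before CPB is open to influence. What remains is the room within the ranges, chiefly FiO2.

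**The primary endpoint is protected and the gain is limited.** Infections are classified by a blinded committee. The team must know the arm from CPB onward whatever the timing, so later allocation removes only the avoidable earlier part. This stands in full.

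**Few patients may be affected.** Surgery is elective, emergencies are excluded, and randomisation is already on the day of surgery. The rate of 1% to 3% is assumed. Nor do these patients necessarily exhaust the reserve of 8: section 8.2 names death during surgery and loss to follow-up, and patients kept in the analysis do not use the reserve. The comparison with 8 matters only if they are dropped.

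**Late randomisation has its own risks.** The team could decide under anaesthesia not to randomise, or could forget. A decision made before the arm is known does not bias the comparison, but missed randomisations are a real cost.

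**Conclusion.** The point holds as a cheap improvement to the design. Randomisation precedes induction, the D0 immune samples and first PaO2/FiO2 follow it, the arms differ only during CPB, and nothing withholds the arm until then. The exposure falls mainly on baseline PaO2/FiO2, for a secondary endpoint.

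The cost of patients who do not reach CPB is roughly 1 to 3 percentage points of power if they are analysed. This rests on an assumed share of 1% to 3% and on their having the control infection rate in both arms.

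A reader might infer that the randomised comparison is compromised. The documents do not support that: allocation before the intervention is valid, no D0 value enters the primary Chi² test, and classification is blinded.

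**What to change.** In section 4.2.2.2 and the schedule table, place the web randomisation, or the opening of the allocation, after the D0 immune samples and the first D0 PaO2/FiO2. It should come as late as feasible before CPB, once the team has confirmed that CPB with aortic clamping will go ahead. In section 4.3, state that the arm is not available to the operating team before that point, and who performs the log-in. Consent stays where it is.

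If randomisation itself stays before induction and only the opening is delayed, name who holds the allocation. State in section 8.5 that every randomised patient is analysed in the assigned arm, including those not put on CPB. Delayed opening protects the baselines but does not keep these patients out of the trial; late randomisation does both.

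The cost is protocol wording, one log-in during the operation (the form can be pre-filled) and occasional missed randomisations. No extra patients or procedures are needed. The change does not prevent deaths after CPB starts or losses to follow-up, and it leaves care from CPB onward unblinded.

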4.2.2.3. Follow-up

Data collected after surgery: duration of procedure, duration of CPB, duration of aortic cross-clamping, antibiotics treatments, duration of MV, length of stay in ICU, hospital length of stay, mortality.

Immunomonitoring parameters (HLA-DR expression, IL-10 and IL-6, lymphocytes count, Indoleamine 2,3-Dioxygenase activity, MDSCs and EV) will be obtained after general anesthesia and before surgery (D0, at 24 hours (D1) and 7 days (D7) (except EV) after surgery.

HLA-DR expression, IL-10, IL-6 and IDO activity will be measured in Rennes.

Ratio of arterial oxygen tension (PaO2) to FIO2 will be obtained before surgery (D0) after induction of anesthesia and 3 h after the end of CPB in the surgical intensive care unit (ICU; under baseline MV settings), and the day after surgery (D1).

Occurrence of postoperative infections within 28 days following cardiac surgery will be monitored. An independent committee blinded to treatment group will ensure the classification of hospital-acquired infections. Antibiotics treatment, length of stay, duration of MV, mortality will be recorded within the first 28 days following surgery.

	Screening Phase	Inclusion Phase (D0) Surgery	D1	D7	D28
Information document	Х				
Clinical Examination (check the selection criteria)	X				
Written informed consent	Х	Or X (later)			
Randomization		Х			
Patient characteristics and clinical data		Х			
Data surgery		Х			
HLA-DR* and MDSCs*		Х	Х	Х	
IL-10*		Х	Х	Х	
IL-6*		Х	Х	Х	
IDO activity*		Х	X	X	

EV*	Х	X		
Lymphocytes count	Х	X	X	
Pa02/Fi02	X After induction of anesthesia and 3 h after the surgery	Х		
Nosocomial infections recording		Х		
Antibiotics treatment	Х			
Lenght of stay X				
Duration of MV		X		
Mortality	Х			
Adverse events recording	X			

* HLA-DR expression, MDSCs, EV, IL-10, IL-6 and IDO activity will be measured in Rennes.

4.3 Description of the measures taken to reduce and prevent bias

4.3.1 Randomization

Randomization will be stratified per centre.

Randomization will be performed in the centres via a webinterface (Ennov Clinical, Ennov Group, Paris, France). A document to help use this tool will be provided to the investigators.

4.3.2 Methods of blinding

This project is a randomized single-blinded (patient) trial.

4.4 Expected duration of participation of persons and description of chronology and of duration of all study periods including monitoring, if applicable

Recruitment period: 24 months

Duration of patient monitoring: 28 days

Duration of analysis of data: 6 months

Estimated total duration of study: 31 months

Starting with inclusion of the first patient, the sponsor has to inform without delay the local health agency and the ethics committee of the actual date of start-up of the study. The actual date of start-up = date of signature of consent form by the first person who is a Patient in the study.

The date of end of the study will be transmitted by the sponsor to the ethics committee and to the local health agency within 90 days or earlier according to local regulations. The date of end of the study corresponds to the last visit of the last person who is a Patient in the study.

